## Evaluation of clinical efficacy of different doses of LT4 in the treatment of pregnant women with normal-high TSH and positive TPOAb in the first half of pregnancy

### **Research background and purpose**

Thyroid hormone (TH) is essential for fetal brain development. The fetal thyroid develops at 8-12 weeks and matures at 18-20 weeks to function. Therefore, fetal development in the first half of pregnancy (gestational age  $\leq$  20 weeks) depends largely on the supply of maternal TH. Normal-high TSH value: It is a thyroid function state unique to women in the pre-pregnancy and pregnancy period; thyroid autoantibodies (mainly TPOAb) during pregnancy reflect the thyroid autoimmune state. TPOAb positivity is considered to be a mild thyroid dysfunction, which can affect placental function through inflammatory reactions such as IL-6, IL-8, IL-10 and tumor necrosis factor  $\alpha$ , and increase the risk of adverse pregnancy outcomes such as miscarriage. The intestinal microbiota also plays a vital role in shaping and regulating the immune system and immune response. Our research group studied the biological characteristics of the intestinal flora in patients with hypothyroidism during pregnancy and abnormal TPOAb and found that abnormal TPOAb was associated with intestinal flora.

Normal-high TSH with positive TPOAb is associated with adverse pregnancy outcomes such as miscarriage, premature birth, premature rupture of membranes, preeclampsia, placental abruption, and fetal growth restriction. Taking levothyroxine (LT4) can reverse the harmful effects of TPOAb and TGAB levels, improve patients' thyroid function, and reduce the incidence of adverse pregnancy outcomes such as gestational diabetes, premature rupture of membranes, miscarriage, premature birth, and macrosomia. The "Guidelines for the Prevention and Management of Thyroid Diseases During Pregnancy and Childbirth" pointed out that in early pregnancy, when TSH is between 2.5mIU/L and the upper limit of the pregnancy reference value (or 4.0mIU/L in early pregnancy) with positive TPOAb, 25ug-50ug LT4 should be given for treatment. However, high-dose LT4 may have adverse reactions such as palpitations, insomnia, sweating, and nausea. Therefore, this study explored the differences in clinical efficacy of different doses of LT4 in the treatment of pregnant women with normal-high TSH and positive TPOAb.

### **Research plan**

#### **1. Research content**

Pregnant women diagnosed with normal-high TSH and positive TPOAb before 20 weeks of pregnancy who received perinatal care and gave birth in the Third Affiliated Hospital of Zhengzhou University from July 2019 to October 2023 were selected and divided into two groups, A and B, with 100 cases in each group according to the dose of LT4 of 25ug and 50ug; those who did not take LT4 were group C, with 200 cases. The clinical efficacy of different doses of LT4 in the treatment of pregnant women with normal-high TSH and positive TPOAb in the first half of pregnancy was explored.

Inclusion criteria: (1) Diagnosed with normal-high TSH and positive TPOAb before 20 weeks of pregnancy (TSH: 2.5mIU/L-upper limit of reference range, TPOAb  $>$  34IU/mL), FT4 in the normal range (FT4: 12-22pmol/L) in line with the diagnostic criteria established by the Laboratory Department of the Third Affiliated Hospital of Zhengzhou University; (2) All subjects voluntarily participated and signed informed consent

Exclusion criteria: (1) Multiple pregnancy (2) Assisted reproductive technology; (3) Suffering from

serious diseases or diseases that affect pregnancy outcomes, such as dysfunction of important organs; (4) Suffering from thyroid disease; (5) Diagnosed with a history of other endocrine, antiphospholipid syndrome and other autoimmune diseases; (6) Taking drugs that affect the thyroid gland (7) LT4 allergy

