## 2. Research steps

- ① Select pregnant women who meet the inclusion and exclusion criteria and group them, and record the basic information of the pregnant women, mainly including: age, height, weight, pregnancy and delivery history, thyroid function and other serological indicators.
- ② Collect blood and stool samples from pregnant women in groups A and B before and after LT4 treatment, track thyroid function indicators such as TSH, FT4, TPOAb before and after treatment in the three groups of pregnant women, and record maternal and fetal nutritional development.
- ③ Pregnancy outcomes: Track and follow up maternal and fetal outcomes, including the incidence and mode of delivery of adverse pregnancy outcomes such as miscarriage, premature birth, gestational hypertension, gestational diabetes, premature rupture of membranes, fetal growth restriction, macrosomia, intrapartum blood loss, neonatal sex, weight, head circumference, height, Apgar score, thyroid disease, etc.
- ④ Statistical methods: SPSS 26.0 software was used for statistical analysis; continuous data were described by (mean  $\pm$  standard deviation), and count data were expressed by frequency and rate; two independent samples that met normal distribution and homogeneity of variance were analyzed by t test and corrected t test; comparison of binary data between two independent samples of count data was analyzed by X test and corrected X test; P < 0.05 was considered statistically significant.

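### Entry is open until 20 weeks and the non-randomised groups are compared without adjustment, so timing is uncontrolled: a first-half effect may be diluted and the A/B/C contrasts are open to confounding

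*Combined protocol and SAP*

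**What the plan says.** Under 1. Research content, the only timing rule for entry is that women be "diagnosed with normal-high TSH and positive TPOAb before 20 weeks of pregnancy". There is an upper limit and no lower one. The aim is worded as LT4 efficacy in the "treatment of pregnant women with normal-high TSH and positive TPOAb in the first half of pregnancy was explored".

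Research background and purpose sets the first half at 20 weeks or less and explains why that period matters: "The fetal thyroid develops at 8-12 weeks and matures at 18-20 weeks to function". The guideline it cites covers a narrower period: "in early pregnancy, when TSH is between 2.5mIU/L and the upper limit of the pregnancy reference value".

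The treated groups are formed "with 100 cases in each group according to the dose of LT4 of 25ug and 50ug", and "those who did not take LT4 were group C, with 200 cases". No randomisation or matching is described, and no start date or duration of LT4 is given.

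Under 2. Research steps, item 1 gives the main baseline data as "age, height, weight, pregnancy and delivery history, thyroid function and other serological indicators". Gestational age at diagnosis and at LT4 start are not named. Item 3 lists miscarriage among many outcomes, with no primary outcome. Item 4 plans two-sample t tests for continuous data and chi-square tests for binary data, with no covariate, stratum or time scale. The Result section reports no significant difference in gestational age between a disease group and a control group.

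**The concern.** The last permitted week of entry coincides with the end of the period the study is about. Women who enter late can have little LT4 inside that period, yet they count the same as women who enter early. Two consequences follow.

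- **Dilution.** If an effect depends on LT4 taken before 20 weeks, pooling late entrants shrinks the average difference between groups. This needs no imbalance, only a material share of late entrants.
- **Confounding by timing.** A later entrant has already passed through part of the period in which miscarriage can occur. If the mix of entry weeks differs between A, B and C, crude incidence differs with no drug effect. Grouping by treatment actually taken does nothing to equalise that mix.

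Both arise even if LT4 starts on the day of diagnosis.

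**Working it through.** **What can be reproduced.** The plan gives group sizes of 100, 100 and 200 but no power, event rate, effect size or entry-week distribution. There is no stated calculation to reproduce. Everything below except those sizes, the 20-week limit and the 0.05 level (taken as two-sided) is an assumption for illustration.

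**1. Exposure before week 20.** Weeks of LT4 = 20 − entry week, if LT4 starts at entry.

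| Entry week | 6 | 8 | 12 | 16 | 18 | 19 |
|---|---|---|---|---|---|---|
| LT4 weeks to week 20 | 14 | 12 | 8 | 4 | 2 | 1 |

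A week-19 entrant has 1/12 of the first-half exposure of a week-8 entrant. If entries were spread evenly over weeks 6 to 20, 8/14 = 57% would enter after week 12 and 2/14 = 14% after week 18.

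**2. Dilution, binary outcome.** Let f be the share of late entrants, the same in both groups. Pooled rate = (1 − f) × early rate + f × late rate. Assume early rates of 12% (C) and 6% (A), and a late rate of 1% in both. At f = 0.5, C is 0.5 × 12 + 0.5 × 1 = 6.5% and A is 0.5 × 6 + 0.5 × 1 = 3.5%. Power is for a pooled-variance test of two proportions, 200 versus 100.

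| f | C | A | Difference (points) | Risk ratio | Power |
|---|---|---|---|---|---|
| 0 | 12.0% | 6.0% | 6.0 | 0.50 | 36% |
| 0.25 | 9.25% | 4.75% | 4.5 | 0.51 | 26% |
| 0.50 | 6.5% | 3.5% | 3.0 | 0.54 | 17% |
| 0.75 | 3.75% | 2.25% | 1.5 | 0.60 | 8% |

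The loss is mainly in the absolute difference and the number of events. The risk ratio moves much less.

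**3. Dilution, continuous outcome, A versus B.** Assume 0.5 SD for week-8 entry, scaled by exposure to 2/12 of that for week-18 entry. Pooled effect = 0.5 × (1 − f) + 0.5 × (2/12) × f. With 100 per group, for f = 0, 0.25, 0.50 and 0.75 the effect is 0.50, 0.40, 0.29 and 0.19 SD, and power is 94%, 80%, 54% and 26%.

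**4. Confounding of crude miscarriage incidence, no drug effect.** Risk from entry to week 20 = 1 − exp(−sum of weekly hazards). Assume 1% per week to week 12 and 0.3% after.

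- Entry at week 8: 1 − exp(−(4 × 0.01 + 8 × 0.003)) = 6.2%.
- Entry at week 14: 1 − exp(−6 × 0.003) = 1.8%.
- An LT4 group with 50% entering at week 14: 0.5 × 6.2 + 0.5 × 1.8 = 4.0%.
- Group C with 30% entering at week 14: 0.7 × 6.2 + 0.3 × 1.8 = 4.9%.
- Ratio, from unrounded values (3.99/4.87): 0.82.

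With a flat hazard of 0.5% per week the two risks are 5.8% and 3.0%, and the ratio is 0.88. The direction reverses if group C holds more late entrants. With 12% early and 1% late, a late share of 40% treated versus 60% control gives 7.6% versus 5.4%, a ratio of 1.41. With 50% in both groups the ratio is 1.00.

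**The case against.** The strongest reply is that the plan is internally consistent if the first half describes when women are diagnosed. Enrolment before 20 weeks then matches the stated population, and pooling across it is a legitimate design choice. That reading is open and it weakens the dilution argument. Unequal time at risk and uncontrolled timing remain.

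A reader might go further than the documents allow in five ways.

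- **That the comparisons are confounded.** This needs entry timing that differs between groups, and no such difference is shown. The Result section even reports similar gestational age in its disease and control groups. That statement gives no time point, does not identify those groups as A, B and C, and rests on a non-significant test, so it does not settle the matter either way.
- **That every contrast is pulled towards zero.** Most listed outcomes occur later in pregnancy or at birth, so LT4 continued past week 20 could still act on them. The background also proposes an inflammatory effect on the placenta with no 20-week limit. Dilution is therefore not uniform.
- **That gestational age was not collected.** The baseline list is explicitly of main items, and the Result section shows that some gestational age was available. The gap is that no planned analysis uses it.
- **That all outcomes are compared as crude rates.** Continuous outcomes get t tests. The shared feature is lack of adjustment.
- **That late entrants have little miscarriage risk left.** No figure for this is given. Moreover, 1. Research content selects women who delivered at the centre, while 2. Research steps counts miscarriage as an outcome. Until these are reconciled, it is unclear how far miscarriage can be observed at any entry week.

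**Conclusion.** The concern holds in a limited form. Entry at any week before 20, grouping by treatment taken, and purely unadjusted tests together leave LT4 time before week 20 and remaining time at risk uncontrolled. This may dilute an effect confined to the first half, and it leaves the A/B/C comparisons open to confounding by timing. It does not show that either has occurred.

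The size cannot be derived from the documents. In the illustrations, half the women entering late halves the absolute difference (6.0 to 3.0 points) but moves the risk ratio only from 0.50 to 0.54. A 20-point difference in late share shifts a null crude miscarriage ratio to between 0.82 and 1.41, depending on direction and assumed hazards. These figures rest on assumed rates, LT4 starting at entry, follow-up of miscarriage to week 20 and complete ascertainment.

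A reader might conclude that the main result should come from early entrants alone. That is not supported. With even entry over weeks 6 to 20, 6/14 = 43% enter by week 12, about 43 women in each LT4 group. At a 6.2% risk that is 43 × 0.062 = 2.7 miscarriages per group, too few to carry the conclusion. The plan also gives no cut-off for such a stratum.

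**What to change.** 1. Take gestational age at diagnosis (all women) and at LT4 start (A and B) from the routine perinatal record, and report their distributions by group.
2. Replace the crude tests with comparisons in the full cohort adjusted for gestational age at diagnosis, by regression or stratified analysis, for continuous and binary outcomes alike. This deals with timing imbalance; it does not undo dilution.
3. Reconcile the selection of women who delivered at the centre with miscarriage as an outcome. Then analyse miscarriage on the gestational-age time scale with delayed entry at diagnosis, so that each woman counts only for the weeks in which she was under observation.
4. Report results by entry period, with a cut-off stated in advance, as a secondary analysis only. This is where any dilution would show.
5. State the time point and the groups behind the gestational-age comparison in the Result section, and state whether the first half refers to diagnosis or to the period of treatment.

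The cost is two dates from existing records, slightly more analysis work and somewhat wider intervals. No extra women or visits are needed, and treatment is unchanged.

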## Feasibility Analysis

Levothyroxine is an effective drug for the treatment of thyroid diseases. It is easily absorbed by the body, has a high utilization rate, and is widely used in clinical practice. The information on the condition of the subjects collected in this study is obtained from routine perinatal care and will not harm their health and rights; the peripheral blood collection in this study is often carried out at the same time as other similar blood test items, without the need for additional blood collection, and the amount of blood collected is small, which causes little harm to the research subjects, and the rest of the samples are collected non-invasively.

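### The plan does not settle whether delivery at the hospital is a condition of entry, and that decides whether miscarriage, a listed outcome, can be observed

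*Combined protocol and SAP*

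**What the plan says.** Two parts of Research content describe who enters the study.

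- **Population sentence.** It covers women "diagnosed with normal-high TSH and positive TPOAb before 20 weeks of pregnancy", and continues "before 20 weeks of pregnancy who received perinatal care and gave birth in the Third Affiliated Hospital", within a window of July 2019 to October 2023. Read literally, a pregnancy that did not end in a birth at the hospital is outside the cohort.
- **Numbered criteria.** Inclusion requires the diagnosis before 20 weeks with laboratory limits, and signed consent. None of the seven exclusion criteria concerns pregnancy loss or delivery elsewhere.

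Research steps, item 1, then says: "Select pregnant women who meet the inclusion and exclusion criteria and group them". It does not mention the birth condition. Item 2 is to "Collect blood and stool samples from pregnant women in groups A and B before and after LT4 treatment", so A and B are labelled before treatment starts. Item 3 follows maternal and fetal outcomes, "including the incidence and mode of delivery of adverse pregnancy outcomes such as miscarriage, premature birth"; miscarriage comes first in the list and is given no gestational-age limit. For binary outcomes, item 4 says that "comparison of binary data between two independent samples of count data was analyzed by" chi-square and corrected chi-square, and names no analysis population or denominator.

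Group sizes are 100, 100 and 200, with no derivation. The Result section reports no pregnancy outcome.

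**The concern.** A woman who is diagnosed at week 9, consents and miscarries at week 12 meets every numbered criterion and fails the population sentence. The plan does not say whether she counts.

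Two things depend on the answer. The first is miscarriage itself, which the background section names both as a harm of the condition and as something LT4 reduces. If birth is required, a finding of no miscarriages would be produced by the entry rule and would say nothing about LT4. The second is the denominator for preterm birth, growth restriction and macrosomia. Requiring birth conditions those comparisons on an event that follows treatment and that, on the plan's own premise, treatment affects.

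**Working it through.** **Inputs from the documents.** A = 100, B = 100, C = 200, total 400; chi-square for binary outcomes; P < 0.05. The documents give no loss rate, effect size or power, so there is no stated figure to reproduce. Loss rates and effects below are assumptions.

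**1. Outcome of the two rules for a woman who miscarries**

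| Rule | Birth at site required? | Is she in the cohort? |
|---|---|---|
| Population sentence | Yes | No |
| Numbered criteria, as used in step 1 | No | Yes |

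The numbered criteria cannot be the complete rule, because site and dates appear only in the population sentence. The birth condition stands in that same clause.

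**2. Birth condition applied.** Miscarriages are about 0/100, 0/100 and 0/200. The word about is needed because miscarriage is undefined and a late loss managed at the hospital might be recorded as a birth. With zero events, the expected count in each event cell is group size × 0 / total = 0. The chi-square statistic divides by that count and is undefined; the corrected form has the same divisor.

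Taken at face value, the zeros would also mislead. One-sided 95% upper limits are:
- 0/100: 1 − 0.05^(1/100) = 3.0%
- 0/200: 1 − 0.05^(1/200) = 1.5%

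Both lie below the loss rates assumed next.

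**3. Birth condition not applied.** Expected losses are n × p, with p the assumed risk after diagnosis, equal in all groups.

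| p | A | B | C | Total | Women needed for 400 births, 400/(1 − p) rounded up |
|---|---|---|---|---|---|
| 5% | 5 | 5 | 10 | 20 | 422 |
| 10% | 10 | 10 | 20 | 40 | 445 |

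**4. Birth outcomes compared among births only.** Let p be the untreated loss risk, rr the ratio by which LT4 changes it, and m the preterm risk of a saved pregnancy relative to the others. Suppose LT4 has no other effect on preterm birth. The apparent ratio, LT4 against none, is

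[(1 − p) + p(1 − rr)m] / [(1 − p) + p(1 − rr)].

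With rr = 0.5:
- p = 0.10, m = 3: (0.90 + 0.15)/0.95 = 1.11
- p = 0.10, m = 0.5: (0.90 + 0.025)/0.95 = 0.97
- p = 0.05, m = 3: (0.95 + 0.075)/0.975 = 1.05
- m = 1, any p: 1.00

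The bias vanishes if LT4 does not change loss or if saved pregnancies carry the usual risk. Otherwise its direction depends on whether m is above or below 1.

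**The case against.** The best defence is that birth cannot be known at selection. Step 1 selects pregnant women, step 2 samples A and B before LT4, and step 3 follows them forward. On that reading the birth phrase only describes the setting. This has force: the phrase may be loose wording, and the steps fit a cohort entered at diagnosis. It does not close the matter. Nothing in the plan withdraws the phrase, and applying it later as an analysis filter would give the same zeros as applying it at entry.

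It is also fair to say that miscarriage is one item in a long list, is not named as primary, and has no reported result. That lowers the severity but leaves the conflict in place.

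A reader might infer two stronger points, which the documents do not support.

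- **That losses were excluded and the reported findings are biased by it.** The documents show an unresolved rule, not how it was applied, and the Result section contains no pregnancy outcome.
- **That women lost between diagnosis and first dose inflate the apparent benefit of LT4**, because group C is defined as "those who did not take LT4 were group C, with 200 cases". This needs losses to be counted, dosing to be delayed, and those women to be moved to C or dropped. The plan describes neither a delay nor such a reassignment. Step 2 labels A and B before treatment, which points to women staying in their group; in that case this mechanism gives no bias.

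**Conclusion.** The conflict is real and should be fixed. Confidence is high for the textual conflict only, not for any effect on results.

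If the birth condition applies, miscarriage cannot be assessed: about 0 of 400 by construction, against 20-40 of 400 at an assumed 5-10% loss after diagnosis. The effect on the other pregnancy outcomes is modest and of uncertain direction: a ratio of about 0.97 to 1.11 if loss is up to 10%, LT4 halves it, and saved pregnancies carry 0.5 to 3 times the usual risk. None of these rates comes from the documents.

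Resolving the conflict makes miscarriage interpretable but does not give it good power. For 100 against 200 women at two-sided 0.05 (the plan does not state sidedness), power to detect a halving is about 15% from an assumed 5% risk and about 30% from 10%.

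**What to change.** **Preferred.**
- Delete the requirement of birth from the population sentence, so that women enter at diagnosis before 20 weeks with consent, whatever the pregnancy outcome.
- State one gestational-age limit for miscarriage.
- Count miscarriage over all enrolled women, each kept in the group given at grouping (Research steps, items 1 and 2).
- Report losses and births elsewhere by group.
- Report delivery-based outcomes among births, and state that condition.

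The definition of group C and the planned chi-square test need not change.

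**Fallback, if early losses cannot be recovered or consented.** State that miscarriage cannot be assessed and make no miscarriage comparison. Label the other pregnancy outcomes as conditional on birth at the hospital. Because this removes a listed outcome from a document that already contains results, disclose it as an outcome change.

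**Cost.** The fallback needs only text and disclosure. The preferred route needs follow-up that may be incomplete. The Feasibility Analysis says "The information on the condition of the subjects collected in this study is obtained from routine perinatal care", so losses managed elsewhere may not be on record, and some neonatal data will be missing for births elsewhere. Since signed consent is an inclusion criterion, adding losses afterwards would need consent or a waiver.

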## Result

(1) There was no significant difference between the disease group and the control group in general conditions such as age, BMI, gestational age, etc.; (2) The disease group had higher TC and LDL levels than the control group, as well as high-sensitivity C-reactive protein (hsCRP) levels, Th17, Th17/Treg ratio was significantly higher than that of the control group, and the percentages of Treg and IL-10 were significantly lower than the control group; (3) TSH, hsCRP, Th17, Th17/Treg ratio, and TNF- $\alpha$  in the disease group after LT4 intervention were significantly higher decreased, and FT4, Treg, and IL-10 increased significantly; (4) The incidence of SIBO in the disease group was higher than that in the control group, and the incidence of SIBO in the disease group after intervention was lower than before intervention; (5) Compared with the HA group, The TSH level of the HB group was lower and the IL-10 level was higher, but there was no significant difference in the levels of blood lipids such as TC, TG, HDL, LDL and other inflammatory factors such as hsCRP and IL-2 between the two groups; (6) Correlation analysis in pregnant women with normal-high TSH values and positive TPOAb: TSH is positively correlated with hsCRP, negatively correlated with Treg proportion, TPOAb is positively correlated with TNF- $\alpha$ ; IL-10 levels are negatively correlated with IL-2 and IL-4 levels; TC is positively correlated with hsCRP.

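### The plan does not say how women came to receive 25ug, 50ug or no LT4, and it describes only unadjusted group comparisons although the main baseline factors are recorded

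*Combined protocol and SAP*

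**What the plan says.** Section 1, Research content, forms the treated groups by dose: women were "divided into two groups, A and B, with 100 cases in each group according to the dose of LT4 of 25ug and 50ug". The comparison group is described by what its members did: "those who did not take LT4 were group C, with 200 cases". Section 2, Research steps, item 1 adds only that eligible women are grouped.

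Entry is open to women "diagnosed with normal-high TSH and positive TPOAb before 20 weeks of pregnancy". The guideline cited in the background concerns early pregnancy and gives a dose range: "or 4.0mIU/L in early pregnancy) with positive TPOAb, 25ug-50ug LT4 should be given for treatment".

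Baseline data are collected. Item 1 of section 2 will "record the basic information of the pregnant women, mainly including: age, height, weight, pregnancy and delivery history, thyroid function", and item 2 will "track thyroid function indicators such as TSH, FT4, TPOAb before and after treatment in the three groups of pregnant women".

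Item 4 covers the analysis. For continuous outcomes, "two independent samples that met normal distribution and homogeneity of variance were analyzed by t test and corrected t test"; for binary outcomes it names chi-square and corrected chi-square tests, with significance at P < 0.05. No adjusted, stratified, matched or weighted group comparison is described.

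The only statement on balance is in the Result section: "There was no significant difference between the disease group and the control group in general conditions such as age, BMI, gestational age, etc".

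**The concern.** The study's aim is the clinical efficacy of different LT4 doses. A crude t or chi-square test answers that question only if the groups would have had similar outcomes without treatment. Random allocation would secure this on average, but the documents do not describe any.

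As worded, the untreated group is defined by treatment taken. The guideline the plan cites recommends treatment in early pregnancy for women with this profile, yet 200 women received none. Unless that was assigned at random, something determined it, and that something may be related to outcome. Gestational week at diagnosis is one candidate, because entry extends to 20 weeks while the guidance concerns early pregnancy. This is an inference; no reason for treating or not treating is documented.

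The entry criteria narrow TSH and FT4 and exclude several diseases. They leave TPOAb titre above 34 IU/mL, previous pregnancy loss, gestational week and TSH within the permitted range free to differ between groups.

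The balance statement does not settle the matter. It compares a disease group with a control group, labels not mapped to A, B and C. It names age, BMI and gestational age, but not TSH, FT4, TPOAb or obstetric history. A non-significant difference is also not evidence of balance.

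**Working it through.** **Inputs.** From the documents: group sizes 100, 100 and 200 (section 1); significance level 0.05 (section 2, item 4), taken as two-sided. The documents give no standard deviations, event rates, baseline differences or correlations, so every other input below is an assumption. The plan has no figure of its own to reproduce; the group sizes come without a sample-size calculation.

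**Continuous outcome, no true effect.** Let the groups differ by d SD on a baseline variable with correlation r to the outcome.

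- Bias of the crude difference = d × r (in SD)
- Standard error = √(1/n₁ + 1/n₂): 0.141 for 100 vs 100; 0.122 for 100 vs 200
- Shift = bias / standard error; false-positive rate = P(|Z + shift| > 1.96)

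Example: d = 0.5, r = 0.3 gives bias 0.15. For 100 vs 100 the shift is 0.15/0.1414 = 1.061 and the rate 18.6%. For 100 vs 200 the shift is 0.15/0.1225 = 1.225 and the rate 23.2%.

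| r | 100 vs 100, d = 0.2 to 0.5 | 100 vs 200, d = 0.2 to 0.5 |
|---|---|---|
| 0.1 | 5.2% to 6.4% | 5.3% to 6.9% |
| 0.2 | 5.9% to 10.9% | 6.2% to 12.9% |
| 0.3 | 7.1% to 18.6% | 7.8% to 23.2% |
| 0.5 | 10.9% to 42.4% | 12.9% to 53.2% |

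For scale, the difference detectable with 80% power is (1.96 + 0.84) × standard error: about 0.40 SD (100 vs 100) and 0.34 SD (100 vs 200). A bias of 0.15 SD is a substantial share of either.

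**Binary outcome, no true effect.** Let a risk factor, for example previous loss, have prevalence q in a group, multiply risk by k, and let women without it have risk b. Group risk = b × (1 + q × (k − 1)). False-positive rates are summed over exact binomial probabilities, first for the uncorrected chi-square test and then with continuity correction throughout.

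| Scenario | Group risks | Crude risk ratio | Uncorrected, 100 vs 100 / 100 vs 200 | Corrected, 100 vs 100 / 100 vs 200 |
|---|---|---|---|---|
| q 30% vs 20%, k 1.5, b 5% | 5.75% vs 5.5% | 1.05 | 4.6% / 5.0% | 2.0% / 2.7% |
| q 40% vs 20%, k 2, b 10% | 14% vs 12% | 1.17 | 7.1% / 8.5% | 4.1% / 5.8% |
| q 40% vs 20%, k 3, b 20% | 36% vs 28% | 1.29 | 23.0% / 29.8% | 18.4% / 25.4% |

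The choice of test changes the false-positive rate but leaves the shifted risk ratio as it is.

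**The case against.** **Allocation may have been assigned.** The documents never say the study was non-randomised. Fixed equal groups of 100 and signed consent would fit assigned dosing. If allocation was random, the crude tests are valid and adjustment mainly adds precision. This stands, and it is why the point is less certain between 25ug and 50ug than against no LT4.

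**The methods list may be incomplete.** The Result section reports a correlation analysis and before-after changes for which item 4 names no method. The safe statement is therefore that no adjusted group comparison is described. The Result section shows none either.

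**Gestational week is a conjecture.** Nothing links it to dose or to non-treatment, and the Result section reports no significant difference in gestational age. That comparison is between unmapped groups and at an unstated time, so it does not exclude the possibility. It does suggest that gestational age was recorded.

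**The magnitudes are assumed and wide.** This is correct. The largest rates need r = 0.5 and d = 0.5. Such a correlation might suit follow-up TSH, but restricting TSH and FT4 at entry generally weakens it, and nothing in the documents supports it for pregnancy outcomes. With continuity correction throughout, the middle binary case falls to 4.1% and 5.8%, so inflation there is small at most. The shifted estimate remains.

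**Eight covariates may be too many, and no primary outcome is named.** Both are fair. The fix therefore allows a short covariate set for rare outcomes.

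**Conclusion.** The concern holds and needs correction before any group difference is read as an effect of LT4. Three facts are firm: no allocation method is stated, only unadjusted two-sample tests are described, and most of the data needed for adjustment are already collected. Non-random allocation itself is inferred, strongly for the untreated group and less so for 25ug against 50ug.

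The direction and size of any bias are unknown. If allocation was not random, P < 0.05 does not hold a 5% error rate for a treatment effect. Across the assumed scenarios the false-positive rate for continuous outcomes ranges from barely above 5% to about half. For binary outcomes, and rarer ones in particular, the harm is mainly a biased risk ratio, 1.05 to 1.29 instead of 1 in the cases examined. These figures illustrate sensitivity and are not estimates for this study.

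**What to change.** 1. State how each woman came to be in A, B or C: random sequence, prescriber's choice, patient's choice or another rule.
2. Make the main comparison a regression on the three-level group factor: ANCOVA for continuous outcomes, logistic or modified Poisson regression for binary ones. Adjust for baseline TSH, log TPOAb, FT4, age, BMI, parity, previous loss and gestational week at entry.
3. For rare outcomes, use a few covariates named in advance (for example TSH, gestational week and previous loss) or three-group propensity weights.
4. Report baseline characteristics by A, B and C with standardised differences, including TSH and TPOAb. Keep the crude tests as descriptive.
5. Unless allocation was random, word conclusions as adjusted associations. Since results are already reported, label the re-analysis post hoc where that applies.

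**Cost.** One statement on allocation, revised analysis wording and a re-analysis of data mostly in hand. Gestational week is not named among the baseline items, although eligibility before 20 weeks requires dating, so its availability must be confirmed. Events limit the model: at an assumed 10% risk, 400 × 0.10 = 40 events. The full model has 2 group terms + 8 covariates = 10 parameters, or 40/10 = 4 events per parameter; the short model has 2 + 3 = 5 parameters, or 40/5 = 8. Unmeasured confounding remains, and a post hoc label weakens what can be claimed.
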